## 7.1 Compound Overview

Lemborexant (LEM) is a novel competitive dual orexin receptor antagonist that is approved for the treatment of insomnia by the Food and Drug Administration (FDA) and Pharmaceuticals and Medical Devices Agency (PMDA) and under development for irregular sleep-wake rhythm disorder. The clinical development program established the safety, tolerability, and efficacy (both short- and long-term) of LEM versus placebo in adult and elderly subjects, including demonstration of respiratory safety in healthy volunteers and subjects with mild OSA (E2006-A001-102; Study 102).

## 7.2 Clinical Experience

Study 102 was a randomized, double-blind, placebo-controlled, crossover study to evaluate the respiratory safety of LEM in adult and elderly ( $\geq 65$  to 90 years) healthy subjects and adult and elderly subjects with mild OSA. In healthy adult and elderly subjects and subjects with mild OSA, compared with placebo, LEM did not decrease peripheral oxygen saturation (SpO2) during total sleep time (TST) after a single dose of treatment, increase the proportion of subjects with at least 1 incident of desaturation (defined as SpO2 <90% for at least 30 seconds during TST compared to placebo, increase the percentage of TST during which SpO2 was <90%; or increased the AHI after a single dose of treatment. Study 102 concluded LEM was well tolerated in healthy adult and elderly subjects, as well as subjects with mild OSA. The approved prescribing information for LEM (Dayvigo®) states that: *“In a study of patients with mild OSA (AHI <15 events per hour of sleep), DAYVIGO did not increase the frequency of apneic events or cause oxygen desaturation.”*

## 7.3 Study Rationale

Per the DAYVIGO approval letter (20 Dec 2019) Eisai was tasked with specific Postmarketing Requirements (PMR), including a request to conduct a randomized, double-blind, placebo-controlled study to evaluate the short-term respiratory safety of LEM in subjects with moderate to severe OSA and in subjects with moderate to severe COPD (PMR 3753-1). The following study is proposed to fulfill this PMR.

# 8 STUDY OBJECTIVES

## 8.1 Primary Objective(s)

### OSA Cohort:

- Using PSG, determine whether lemborexant increases the AHI on Day 8 of treatment in adult and elderly subjects (adults  $\geq 45$  to <65 years; elderly  $\geq 65$  to 90 years) with moderate to severe obstructive sleep apnea (OSA) compared with placebo

**COPD Cohort:**

- Using pulse oximetry, determine whether lemborexant decreases mean SpO2 during TST on Day 8 of treatment in adult and elderly subjects (adults  $\geq 45$  to  $< 65$  years; elderly  $\geq 65$  to 90 years) with moderate to severe COPD compared with placebo

**8.2 Secondary Objective(s)**

**OSA Cohort:**

- Using PSG, determine whether lemborexant increases the AHI on Day 1 of treatment compared with placebo
- Using pulse oximetry, determine whether lemborexant decreases the mean SpO2 during TST on Days 1 and 8 of treatment compared with placebo
- Using pulse oximetry, determine whether lemborexant increases the percentage of TST during which the SpO2 is  $<90\%$ ,  $<85\%$ , and  $<80\%$  on Days 1 and 8 of treatment compared with placebo
- Using pulse oximetry, determine whether lemborexant increases the mean oxygen desaturation index (ODI) on Days 1 and 8 of treatment compared with placebo (revised per Amendment 01)
- Using pulse oximetry, determine whether lemborexant increases the absolute number of desaturations ( $\geq 3\%$  reduction from Baseline SpO2) on Days 1 and 8 of treatment compared with placebo (revised per Amendment 01)
- Evaluate safety and tolerability of lemborexant compared with placebo

**COPD Cohort:**

- Using pulse oximetry, determine whether lemborexant decreases mean SpO2 during TST on Day 1 of treatment compared with placebo
- Using PSG, determine whether lemborexant increases the AHI on Days 1 and 8 of treatment compared with placebo
- Using pulse oximetry, determine whether lemborexant increases the percentage of TST during which the SpO2 is  $<90\%$ ,  $<85\%$ , and  $<80\%$  on Days 1 and 8 of treatment compared with placebo
- Using pulse oximetry, determine whether lemborexant increases the mean ODI on Days 1 and 8 of treatment compared with placebo (revised per Amendment 01)
- Using pulse oximetry, determine whether lemborexant increases the absolute number of desaturations ( $\geq 3\%$  reduction from Baseline SpO2) on Days 1 and 8 of treatment compared with placebo (revised per Amendment 01)
- Evaluate safety and tolerability of lemborexant compared with placebo

### **8.3 Exploratory Objective(s)**

#### **OSA and COPD Cohorts:**

Explore the effects of lemborexant compared with placebo on the following for Days 1 and 8 of treatment:

- The mean SpO2 during rapid eye movement (REM) sleep, non-REM (NREM) sleep, and wake
- AHI during REM and NREM sleep
- Determine whether lemborexant increases the AHI, and decreases the mean SpO2 during TST separately for adult and elderly subjects
- Plasma concentrations of lemborexant and its metabolites (M4, M9, and M10)
- Explore the effect of lemborexant on blood biomarkers potentially related to dementia, OSA, and/or COPD

[figure not shown]
## **9 INVESTIGATIONAL PLAN**

### **9.1 Overall Study Design and Plan**

In both the OSA and COPD Cohorts, this will be a randomized, double-blind, placebo-controlled, 2-period crossover study. There will be 2 phases, Prerandomization and Randomization. The Prerandomization Phase will last up to 21 days and will consist of the Screening Period and Baseline Period. In the Randomization Phase subjects will be randomized in treatment sequences A or B (OSA Cohort), or treatment sequences C or D (COPD Cohort) consisting of 2 Treatment Periods, each of 8 days duration, separated by a washout interval of at least 14 days, and a Follow-up Period of approximately 28 days. Twenty-eight days after the final study dose, there will be an end of study (EOS) Visit.

At specified visits throughout the Prerandomization Phase and the Randomization Phase, all subjects will undergo routine safety assessments, including 12-lead ECG, physical examination, vital signs, weight, hematology, blood clinical chemistry analysis, urinalysis, reporting of AEs, and assessment of suicidality. At each clinic visit, subjects will also undergo a urine drug screen.

Approximately 75 subjects each will be screened for OSA and COPD cohorts in order to ensure that a total of 30 evaluable subjects complete the study in each cohort (20 evaluable adult subjects [ $\geq 45$  and  $< 65$  years] and 10 evaluable elderly subjects [ $\geq 65$  to 90 years]). Discontinued subjects may be replaced to ensure 20 adults and 10 elderly subjects complete both Treatment Periods. However, subjects who discontinue for a serious adverse drug reaction (SADR) cannot be replaced.

**Figure 1 Study Design for OSA and COPD Cohorts (revised per Amendment 01)**

BL1 = Period 1 Baseline, BL2 = Period 2 Baseline, COPD = chronic obstructive pulmonary disease, EOS = End of Study, ET = Early Termination, OSA = Obstructive sleep apnea, S = Sleep laboratory, R = Randomization, UN = Un-Scheduled visit.

a: Visit 1A only applies to subjects being evaluated for the COPD Cohort, in whom spirometry is required. Spirometry may be performed at the study site, or offsite, so long as a final report is available for review at the study site by Visit 2

b: Telephone visit

c: Assessments as shown will be conducted at the EOS visit and for subjects who discontinue the study early after Visit 3. At the end of the Follow-up Period, subjects will return to the clinic for an EOS visit. If subjects discontinue prematurely, they will undergo an ET Visit and will then be followed for 28 days, after which, an EOS visit should be scheduled.

d: The assessments at an Unscheduled Visit will be conducted at the Investigator's discretion.

e: Visit must be followed by a washout interval of at least 14 days in duration. This may be extended by up to 2 days if necessary to accommodate a weekend, in which case, subsequent visits will be up to 2 days later than target.

### 9.1.1 Prerandomization/Pretreatment Phase

The Prerandomization Phase will include a Screening Period and a Baseline Period.

#### 9.1.1.1 Screening Period

The Screening Period will begin no more than 21 days before the subject is randomized and during which informed consent will be obtained after the study has been fully explained to the subject and before the conduct of any screening procedures or assessments. Subjects eligible for the COPD Cohort will then undergo screening spirometry between Visit 1 and Visit 2 (designated Visit 1A), which may be performed at the study site, or offsite, so long as a final report is available for review at the study site by Visit 2. Spirometry will be performed based on Global Initiative for Obstructive Lung Disease (GOLD) recommendations ([Appendix 2](#)).

After at least 6 days of the initial Screening visit, (to allow subjects the opportunity to complete the sleep diary for at least 5 nights), subjects will return to the clinic for the second Screening Visit to undergo PSG. For subjects being evaluated for the COPD Cohort, results of screening spirometry will also be reviewed.

Subjects who continue to meet the eligibility criteria will remain overnight in the sleep laboratory. The mean habitual bedtime (MHB) will be calculated from the most recent 5 days of the subject's sleep diary. This will be used to determine bedtime ("lights off"). The PSG recording will begin at lights off and will continue for 8 hours (until lights on). The end of the 8-hour PSG recording will be defined as waketime ("lights on"). Subjects may leave the clinic after the investigator determines that it is safe for them to do so.

The PSG will be reviewed for exclusion criteria related to OSA severity (only mild for the OSA Cohort, and moderate to severe for the COPD Cohort), periodic limb movement disorder, and parasomnias. The pulse oximetry recording will be reviewed for exclusion criteria related to oxygen desaturation.

Subjects who continue to meet the eligibility criteria will enter the Baseline Period.

#### 9.1.1.2 Baseline Period

At the Baseline Period (1 day) eligible subjects will be admitted to the clinic. After completion of routine safety assessments, including the Columbia-Suicide Severity Rating Scale (C-SSRS), blood samples will be collected for the exploratory analyses related to potential dementia, COPD, and OSA-related biomarkers. Subject will then enter the Randomization Phase.

#### 9.1.2 Randomization/Treatment Phase

In the Randomization Phase, subjects will be randomized into treatment sequence A or B (OSA Cohort), or treatment sequence C or D (COPD Cohort) consisting of 2 Treatment Periods, 8 nights duration each: lemborexant 10 mg and placebo, with the treatments periods separated by a washout interval of at least 14 days. Randomization will be stratified by age (adults  $\geq$ 45 and  $<$ 65 years, vs elderly  $\geq$ 65 to 90 years). A sufficient number of subjects will be randomized to ensure that, for each Cohort, 20 evaluable adult subjects and 10 evaluable

elderly subjects complete the study. Within each age stratum, subjects will be randomized to 1 of the 2 treatment sequences in a 1:1 ratio and enter Treatment Period 1.

Subjects will remain overnight in the sleep laboratory. Bedtime (lights off) will be at the MHB that was used at the second Screening Visit (Visit 2). Subjects will receive study drug immediately (within 5 minutes) before lights off. The PSG recording will begin at lights off and will continue for 8 hours (until lights on). The following morning, a PK blood sample will be collected and vital signs assessed, as indicated in the Schedule of Procedures/Assessments ([Table 4](#)).

Subjects will be provided with study medication to be administered for 6 consecutive nights at home, and will be instructed to take the medication immediately (within 5 minutes) before bedtime. Subjects will also be instructed on study restrictions related to prohibited medications/drugs, caffeine and alcohol, and the prohibitions regarding the use of continuous positive airway pressure (CPAP) device or dental appliance. If  $\text{SpO}_2 < 80\%$  for  $\geq 20\%$  of TST during the first night of treatment, the subject must be early terminated. Subjects may leave the clinic after the investigator determines that it is safe for them to do so. Subjects will be instructed to promptly contact study physician in case of any new complaints or exacerbation of current symptoms.

On Day 5 (with a window of  $\pm 2$  days to accommodate a weekend), the site will telephone the subject to assess AEs and record concomitant medications. If any AE is clinically significant and requires follow-up, an Unscheduled Visit should be arranged as soon as possible.

After 6 consecutive nights of administering study drug at home, subjects will return to the clinic and receive 8th dose of study drug at the sleep laboratory within 5 min before the lights off and will remain overnight in the sleep laboratory. Subjects will undergo the same procedures as on Day 1 (including urine pregnancy test for female subjects of childbearing potential and urine drug test), in addition to which, a blood sample for pre-dose (trough) PK will be taken within 1 hour before dosing. The following morning, blood samples will be collected for PK, and exploratory biomarker assessments. Routine safety assessments will also be conducted, as indicated in the Schedule of Procedures/Assessments ([Table 4](#)). Subjects will be instructed on study restrictions related to prohibited medications/drugs, alcohol and caffeine, and the prohibitions regarding the use of CPAP device or dental appliance. Subjects may leave the clinic after the investigator determines that it is safe for them to do so.

After Treatment Period 1, there will be a washout interval of at least 14 days. After the washout interval, subjects will return to the clinic for Treatment Period 2, which will follow the same schedule and procedures as did in Treatment Period 1, including re-review of inclusion and exclusion criteria, and oxygen desaturation. However, spirometry will only be performed during the Screening Period (revised per Amendment 01).

At specified visits throughout the Prerandomization Phase and the Randomization Phase, all subjects will undergo routine safety assessments, including 12-lead ECG, physical examination, vital signs, weight, hematology, blood clinical chemistry analysis, urinalysis,

reporting of AEs, and assessment of suicidality. At each clinic visit, subjects will also undergo a urine drug screen.

#### 9.1.2.1 Follow-Up Period

During the Follow-up Period (approximately 28 days), subjects will not receive any treatment. At the end of the Follow-up Period, subjects will return to the clinic for an EOS visit at which safety will be assessed.

If subjects discontinue prematurely, they will undergo an Early Termination (ET) Visit and will then be followed for 28 days, after which, an EOS visit should be scheduled.

## 9.2 Discussion of Study Design, Including Choice of Control Groups

### Dose Selection

The approved dose of LEM 10 mg was chosen based on the safety and efficacy studies from the clinical development program.

### Justification of the Endpoints

The primary analysis in the OSA Cohort compares the mean AHI (assessed by PSG) on the final night of LEM dosing with the AHI on the final night of placebo dosing. The AHI is the index by which OSA is diagnosed, is used to categorize the severity of disease, and is the standard primary endpoint in clinical studies of the safety of drugs in patients with OSA; for example, this was used for LEM Study 102, suvorexant ([Sun, et al., 2016](#)), ramelteon ([Kryger, et al., 2007](#)), and eszopiclone ([Rosenberg, et al., 2007](#)). Like the study of suvorexant, Study 113 will use the mean AHI at the end of each treatment period as the primary endpoint, as LEM will have reached steady state.

The primary analysis in the COPD Cohort compares mean SpO2 over total sleep time (TST) on the final night of LEM dosing with mean SpO2 during TST on the final night of placebo dosing. Specifically, a 2% decrease in mean SpO2 during TST is considered a clinically meaningful change. SpO2 measures hypoxia, which can serve as a proxy for hypoventilation during sleep ([Piper and Yee, 2014](#)). In the ramelteon study of subjects with moderate to severe COPD ([Kryger, et al., 2009](#)), the mean SpO2 during TST at baseline was 92.6%, thus a 2% or greater decrease from 92% could result in hypoxia (SpO2 <90%). Of note, this was also used as the primary endpoint in the suvorexant study ([Sun, et al., 2015](#)).

### Justification of the sample size for the OSA cohort

In the suvorexant study, 26 subjects with mild to moderate OSA were studied; in Study 102, 30 subjects with mild OSA were evaluated. This was acceptable to FDA and PMDA. Thus, the proposed sample size for Study 113 OSA is 30 ([Sun, et al., 2016](#)).

## **Inclusion and Exclusion Criteria for the OSA and COPD Cohorts**

The eligibility criteria in Study 113 are largely standard for safety studies in subjects, with particular criteria that are standard for studies of sleep agents (exclusion of significant periodic limb movement disorder or parasomnias; certain restrictions on habitual bedtime). Insomnia disorder is not specifically excluded unless subjects habitually sleep less than 5.5 hours. The screening PSG will be key for inclusion, since subjects tend to sleep less well in a sleep laboratory than at home. This is important since the AHI tends to be higher during REM sleep, which is more frequent during the second half of the night, the time when elderly poor sleepers tend to be awake.

Of note, CPAP and oral devices will be prohibited throughout the study. The study requires uncorrected values for AHI. The phenomenon of “CPAP washout” has been reported, in which, following cessation of CPAP use, AHI increases gradually over days or weeks ([Vroegop, et al., 2015](#)). Although the existence of this phenomenon is not universally accepted, there is no doubt that daytime sleepiness increases when CPAP is stopped, and those patients with OSA will accommodate to the increased levels of sleepiness, but that takes time, and the duration varies among patients. To avoid dosing with LEM (which may cause somnolence during the day in some subjects) against an unstable baseline of daytime sleepiness, Study 113 requires that CPAP not be used from 2 weeks before the screening PSG until the end of the second treatment period. This should not interfere with the medical care of OSA patients, or be a significant impediment to recruitment; many patients do not tolerate CPAP, such that non-compliance rates are high, as stated above. Further, the exclusion criterion specifies that there must not be a requirement that subjects use CPAP during the study, thereby excluding any for whom CPAP is a medical necessity. Whether subjects had been prescribed CPAP or other treatments for OSA in the past will be noted at Screening.

## **Inclusion and Exclusion criteria for the COPD Cohort**

The COPD cohort will include subjects with moderate to severe COPD and an AHI <15 based on PSG. A diagnosis of mild OSA is permissible, as OSA is a common co-morbidity in patients with COPD, and high-level evidence for the benefit of mild OSA treatment is sparse ([Gay, et al., 2006](#)). Subjects will also be required to have a SpO2 during wakefulness greater than 90% (both supine and sitting), and a SpO2 during sleep ≥80% for at least 75% of the recording period with no more than five continuous minutes less than 80% and with no SpO2 readings less than 70%. These criteria are similar to the ramelteon study in subjects with moderate to severe COPD ([Kryger, et al., 2009](#)). Subjects who use continuous oxygen therapy (>16 hours per day) or who, in the opinion of the investigator, the removal of oxygen therapy could affect the subject’s safety or interfere with the study assessments, are also excluded, which also aligns with prior respiratory safety studies in COPD.

### **9.3 Selection of Study Population**

Subjects who do not meet all of the inclusion criteria or who meet any of the exclusion criteria will not be eligible to receive study drug.

### 9.3.1 Inclusion Criteria

Subjects must meet all of the following criteria to be included in this study (OSA and COPD cohorts):

1. Male or female, age  $\geq 45$  and  $\leq 90$  at the time of informed consent
2. Voluntary agreement and ability to provide written informed consent
3. Body mass index (BMI)  $<40 \text{ kg/m}^2$
4. Reports habitually sleeping for at least 5.5 hours per night
5. Reports habitual bedtime between 21:00 and midnight
6. Agrees to stay in bed for 7 hours per night for the duration of the study
7. At Screening Visit 2: Has completed the sleep diary for at least 5 consecutive nights
8. At Screening Visit 2: Confirmation of MHB between 21:00 and midnight (sleep diary)

Additional Inclusion Criteria (OSA Cohort)

9. Moderate to severe OSA diagnosed according to the criteria of the ICSD, confirmed by PSG (home sleep testing by portable monitor is acceptable) within the previous 5 years or a repeated PSG during screening
10. On screening PSG: moderate OSA (defined as  $15 \leq \text{AHI} < 30$ ) or severe OSA (defined as  $\text{AHI} \geq 30$  per hour)
11. SpO2  $\geq 94\%$  assessed as part of vital signs at Screening Visit 1

Additional Inclusion Criteria (COPD Cohort)

12. Screening spirometry performed as per the GOLD recommendations
13. On screening spirometry, based on post-bronchodilator Forced Expiratory Volume in 1 second (FEV1):
  - FEV1/Forced Vital Capacity (FVC)  $< 0.70$  and one of the following:
    - $50\% \leq \text{FEV1} < 80\%$  predicted (GOLD 2 Classification for moderate COPD) or
    - $30\% \leq \text{FEV1} < 50\%$  predicted (GOLD 3 Classification for severe COPD)
14. Moderate to severe COPD according to medical history and screening spirometry as per the GOLD criteria (GOLD 2019)
15. On screening PSG
  - AHI  $< 15$
  - SpO2 during wakefulness  $> 90\%$  (both supine and sitting)
  - SpO2 during sleep  $\geq 80\%$  for at least 75% of the recording period with no more than five continuous minutes  $< 80\%$  and with no SpO2 readings  $< 70\%$

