### 9.3.2 Exclusion Criteria

1. Females of childbearing potential

NOTE: All females will be considered to be of childbearing potential unless they are postmenopausal (amenorrheic for at least 12 consecutive months, in the appropriate age group, and without other known or suspected cause) or have been sterilized surgically (ie,

bilateral tubal ligation, total hysterectomy, or bilateral oophorectomy, all with surgery at least 1 month before dosing).

2. A current diagnosis of restless legs syndrome, periodic limb movement disorder, circadian rhythm sleep disorder, or narcolepsy
3. Reports symptoms potentially related to narcolepsy, that in the clinical opinion of the investigator indicate the need for referral for a diagnostic evaluation for the presence of narcolepsy
4. A history of symptoms of REM Behavior Disorder, sleep-related violent behavior, sleep-driving, or sleep-eating, or symptoms of another parasomnia that in the investigator's opinion make the subject unsuitable for the study
5. Periodic Limb Movement with Arousal Index (PLMAI) as measured on the screening PSG:
  - Age 18 to <65 years: PLMAI  $\geq 10$
  - Age  $>65$  years: PLMAI  $>15$
6. A prolonged QTcF interval (QTcF  $>450$  ms) as demonstrated by a repeated ECG at Screening
7. Any suicidal ideation with intent with or without a plan at Screening or within 6 months of Screening (ie, answering "Yes" to questions 4 or 5 on the Suicidal Ideation section of the C-SSRS)
8. Any lifetime suicidal behavior (per the Suicidal Behavior section of the C-SSRS) within 10 years of Screening
9. Evidence of clinically significant disease (eg, cardiac, respiratory, gastrointestinal, renal disease) that in the opinion of the investigator(s) could affect the subject's safety or interfere with the study assessments
10. Hypersensitivity to the study drug or any of the excipients
11. Used any prohibited prescription or over-the-counter medications within 1 week or 5 half-lives, whichever is longer, before the screening PSG
12. Any history of or concomitant medical condition that in the opinion of the investigator(s) would compromise the subject's ability to safely complete the study
13. Scheduled for surgery during the study that requires general anesthesia or administration of prohibited medications
14. Psychotic disorder(s) or unstable recurrent affective disorder(s) evident by use of antipsychotics or prior suicide attempt(s) within approximately the last 2 years

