15. History of drug or alcohol dependency or abuse within approximately the last 2 years
16. Use of illegal recreational drugs (includes marijuana, regardless of whether prescribed for medicinal use)
17. Currently enrolled in another clinical study or used any investigational drug or device within 28 days or 5 $\times$  the half-life, whichever is longer preceding informed consent
18. Previously participated in other clinical trial of lemborexant
19. Exposure within the last 14 days to an individual with confirmed or probable corona virus disease 2019 (COVID-19) or symptoms within the last 14 days that are on the most

recent Centers for Disease Control and Prevention (CDC) list of COVID symptoms or any other reason to consider the subject at potential risk for an acute COVID-19 infection (revised per Amendment 01)

Additional Exclusion Criteria (OSA Cohort)

20. SpO2 <80% for  $\geq 5\%$  of TST during the screening PSG
21. Use of a CPAP device or dental appliance within 2 weeks of the screening PSG, and does not agree to abstain from the use of a CPAP device or dental appliance from the Screening Visit through the last study visit
22. Current evidence of a clinically significant, active respiratory disorder other than OSA. This includes bronchiectasis, emphysema, asthma, COPD or any other pulmonary disorder identified by review of medical history, physical examination, and which in the opinion of the investigator, could compromise the subject's safety or interfere with study assessments.
23. Current evidence of other clinically significant disease (eg, psychiatric disorders, disorders of the gastrointestinal tract, liver, kidney, respiratory system, endocrine system, hematological system, neurological system, cardiovascular system, or a congenital abnormality), malignancy within the past 5 years (other than adequately treated basal cell carcinoma or in situ carcinoma of the cervix), or chronic pain that in the opinion of the investigator could affect the subject's safety or interfere with the study assessments. Subjects for whom a sedating drug would be contraindicated for safety reasons because of the subject's occupation or activities are also excluded. Subjects with insomnia disorder, who complain of difficulties with sleep onset and/or sleep maintenance, are eligible provided that they meet this criterion. Note that medications to treat insomnia are prohibited.

Additional Exclusion Criteria (COPD Cohort)

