24. Use of continuous ( $>16$  h/day) oxygen therapy
25. Use of oxygen therapy during PSG
26. Determination that, in the opinion of the investigator, removal of oxygen therapy could affect the subject's safety or interfere with the study assessments
27. Recent changes to COPD medications or recent acute exacerbation of COPD (ie, needing hospitalization or treatment with oral corticosteroids and/or antibiotics) within 3 months of enrollment (revised per Amendment 01)
28. On screening spirometry:
  - FEV1/FVC  $\geq 0.70$
  - FEV1  $\geq 80\%$  predicted (GOLD 1 Classification for mild COPD)
  - FEV1  $<30\%$  predicted (GOLD 4 Classification for very severe COPD)
29. On screening PSG:
  - Moderate to severe OSA (AHI  $\geq 15$ )
  - SpO2 <90% during wakefulness (supine and sitting)
  - SpO2 during sleep <80% for 25% or more of the recording with  $>5$  consecutive minutes <80% and any SpO2 reading <70%
30. ECG evidence of right ventricular hypertrophy or right heart failure

31. Screening hematocrit >55%
32. Use of a CPAP device or dental appliance within 2 weeks of the screening PSG, and does not agree to abstain from the use of a CPAP device or dental appliance from the Screening Visit through the last study visit
33. Current evidence of a clinically significant, active respiratory disorder other than COPD and mild OSA. This includes any other pulmonary disorder identified by review of medical history, physical examination, and which in the opinion of the investigator, could compromise the subject's safety or interfere with study assessments.

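### COPD entry sets no limit on screening SpO2 below 80% as a share of total sleep time, so a subject already at the first-night stopping limit can meet every numeric criterion

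*Protocol*

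**What the plan says.** **COPD entry.** Inclusion criterion 15 (Protocol 9.3.1, repeated in the Synopsis and in section 9.2) requires SpO2 during sleep to be at least 80% "for at least 75% of the recording period with no more than five continuous minutes" below 80% and no reading below 70%. The same criterion requires AHI below 15 and wake SpO2 above 90%. Exclusion 29 (Protocol 9.3.2) also uses the recording as its denominator: SpO2 "during sleep <80% for 25% or more of the recording with" a run longer than 5 minutes and a reading under 70%. Because those conditions are joined, exclusion 29 is no stricter than inclusion 15.

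**First-night stop.** Protocol 9.1.2 and the Synopsis say that if SpO2 is below 80% for at least 20% "of TST during the first night of treatment, the subject must be early terminated". The rule is not confined to one cohort.

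**OSA entry, for comparison.** Exclusion 20 removes an OSA subject with SpO2 below 80% for at least 5% "of TST during the screening PSG". This is the only screening limit written as a share of TST, and it sits under the OSA heading.

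**Screening review.** Protocol 9.1.1.1 states: "The pulse oximetry recording will be reviewed for exclusion criteria related to oxygen desaturation".

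**The concern.** A stopping limit should not be reachable at entry by someone who satisfies every numeric criterion. In the OSA cohort the entry limit (5% of TST) lies well under the stopping limit (20% of TST), on the same scale. In the COPD cohort the entry limit is on another scale, and its nominal value, 25%, is the larger number.

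Three things would follow for a COPD subject who enters at or past the stopping limit and whose first night repeats screening:

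- The subject takes study drug and must then be terminated for a state already on file. The screening polysomnogram is the only one before dosing, since footnotes q and r of Table 4 place both baseline-day recordings after study drug.
- The stop applies whatever was taken that night, so it could occur on placebo and would say nothing about the drug.
- A subject stopped in Period 1 has no Day 8 value, and Day 8 mean SpO2 is the COPD primary endpoint. Section 9.1 allows replacement, but that means exposing another subject.

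**Working it through.** The plan gives no figure to reproduce here. The check puts both limits on one scale.

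**Inputs**

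- Recording length: 8 hours = 480 minutes (Protocol 9.1.1.1).
- Entry: at least 75% of the recording, so 0.75 × 480 = 360 minutes, leaving at most 120 minutes.
- Stop: 20% of TST (Protocol 9.1.2).
- TST on the screening night: not given. It is **assumed** to lie between 330 and 480 minutes. The lower end is the 5.5 hours of habitual sleep in inclusion 4, which is a reported habit and not a minimum on the recording.

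**Three readings of criterion 15**

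- A, share of the recording: time below 80% may reach 120 minutes, so the largest share of TST is 120/TST.
- B, share of sleep: the largest share is 25% of TST.
- C, strictest literal reading: 360 minutes must be both asleep and at 80% or more, so the largest share is (TST − 360)/TST.

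| TST (min) | Stop limit, 0.20 × TST (min) | Stop limit as % of 480 min | Largest share of TST at entry: A | B | C |
|---|---|---|---|---|---|
| 330 | 66 | 13.75% | 36.4% | 25% | cannot qualify |
| 400 | 80 | 16.7% | 30.0% | 25% | 10.0% |
| 440 | 88 | 18.3% | 27.3% | 25% | 18.2% |
| 450 | 90 | 18.75% | 26.7% | 25% | 20.0% |
| 460 | 92 | 19.2% | 26.1% | 25% | 21.7% |
| 480 | 96 | 20.0% | 25.0% | 25% | 25.0% |

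Under A and B the entry maximum exceeds 20% at every TST. Under C it reaches 20% when (TST − 360)/TST = 0.20, that is TST = 360/0.80 = 450 minutes, a sleep efficiency of 450/480 = 93.75%.

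**Do the other conditions close the gap?**

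- *Five-minute limit.* The stopping limit needs at least 66/5, rounded up to 14, separate episodes at TST 330, and 96/5, rounded up to 20, at TST 480. Under C the range is 90/5 = 18 to 20.
- *AHI below 15.* This allows fewer than 15 × 330/60 = 82.5 events, so 82, at TST 330, and fewer than 15 × 480/60 = 120, so 119, at TST 480. Both are far above 14–20.
- *A constructed night that passes all three readings.* Take TST 460 minutes, 24 episodes of 4 minutes at 76%, other sleep at 88% and wake at 93%. Time below 80% is 24 × 4 = 96 minutes, and 96/460 = 20.9% of TST. Sleep at 80% or more is 460 − 96 = 364 minutes, and 364/480 = 75.8% of the recording. The longest run is 4 minutes and the lowest reading is 76%. If every episode is scored as a respiratory event, AHI is 24/(460/60) = 3.1. Inclusion 15 is met and exclusion 29 is not triggered, yet the stopping limit is passed.

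**The case against.** The strongest reply is that the overlap is narrow. The recording-based limit does cap the share of TST indirectly. On the most literal reading (C), the overlap needs at least 450 minutes of sleep in 480, and section 9.2 itself observes that "subjects tend to sleep less well in a sleep laboratory than at home". This stands as a statement about frequency. It does not remove the overlap, because the indirect cap (25%, or 120/TST) lies above 20%. Reading C would also bar anyone sleeping under 360 minutes whatever their saturation, although inclusion 4 accepts a habit of 330 minutes.

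The other conditions also bind more than the episode counts suggest. If every episode is scored as a respiratory event, AHI below 15 means the episodes must average at least about 48 seconds (66 × 60/82 = 48.3; 96 × 60/119 = 48.4), and none may exceed 5 minutes. That narrows the profile without excluding it.

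Investigator judgement could keep such a subject out. Exclusion 12, for example, covers "Any history of or concomitant medical condition that in the opinion of the investigator(s) would compromise" safe completion, and exclusions 9, 26, 33 and 34 also turn on opinion. They could act but need not. Exclusions 30 (ECG evidence of right heart disease) and 31 (hematocrit above 55%) do not constrain the overnight oximetry.

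Section 9.2 gives a rationale: "These criteria are similar to the ramelteon study in subjects with moderate to severe COPD". That explains where the criteria came from but does not relate them to this protocol's stopping rule.

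Finally, the harm is limited. At worst the subject has one laboratory-supervised dose in that period before removal, and may be replaced unless the discontinuation was for a serious adverse drug reaction. This is why the point is minor.

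**Conclusion.** The concern holds. No numeric COPD entry criterion keeps screening time below 80% under 20% of TST. A subject at or past the first-night stopping limit can satisfy all of them on every reading of criterion 15: at any TST in the assumed range under readings A and B, and only at TST of 450 minutes or more under C.

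The size in practice is unknown. It depends on how many COPD subjects desaturate in at least 14–20 separate short episodes while keeping wake SpO2 above 90% and every reading at 70% or more. It also depends on how well screening repeats on night one. The documents contain no data on either. Such subjects should be rare. Severity is minor: the case for change rests on avoiding a foreseeable dose-then-terminate sequence at almost no cost, not on a demonstrated effect on the primary estimate.

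**What to change.** Add a COPD exclusion in the form of OSA exclusion 20: SpO2 below 80% for 20% or more of TST on the screening polysomnogram. Restate the desaturation limits in inclusion 15 and exclusion 29 on the TST scale so that all three agree, and carry the change into the Synopsis and section 9.2.

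A cut-off at exactly 20% still admits a subject at 19%, who could cross the limit on night one through ordinary variation. Whether to set a lower limit for that reason is the sponsor's choice.

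The cost is one added line and matching wording. No new assessment is needed, because the screening oximetry is already reviewed for desaturation. A few more COPD screen failures are possible.
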